Study Protocol and Statistical Analysis Plan

The impact of leg movement on the skin to adductor canal distance: a potential cause for catheter displacement?

NCT 03562559

April 15th 2019

Objectives:

The primary goal of this study was to discover if there is significant change in the distance from the skin to the adductor canal with typical movements that happen after total knee arthroplasty. The secondary goals were to see absolute skin to adductor canal distance and if these changes in distance had any relation to the BMI and leg circumference.

Background Information:

Total knee arthroplasty (TKA) is increasingly common in North America due to growing obesity rates and an aging population¹. Effective pain control using a multimodal approach decreases narcotic use, enhances patient satisfaction and leads to quicker recovery². Regional anesthetic techniques such as the adductor canal block (ACB) have become a major component of the pain management strategy post TKA³⁻⁵.

Single injection ACB and continuous infusion via a catheter are both currently utilized with the latter conferring the theoretical benefit of prolonged analgesia⁶. The efficacy of catheter analgesia is predicated primarily on its proper placement and maintenance. Despite growing expertise and the use of ultrasound, catheter tip displacement has been reported as high as 26%⁷⁻⁸. In addition, recent trials did not show clear benefit of ACB catheters over single injections in terms of opioid consumption⁹ and pain scores¹⁰. This observational study seeks to investigate simple anatomic and mechanical factors that may contribute to catheter failure. Specifically, the trial examines the average SAC distance, and measures the relative distance changes as the leg is moved in various positions. It is hypothesized that the SAC distance changes with leg movement. If so, one may infer that repeated leg movements could gradually cause catheter tip migration while the catheter is secured to a fixed point on the skin.

Study Design and Methods:

After gaining ethics approval from the University of British Columbia (H17-02633) and registration with ClinicalTrials.gov (NCT 03562559) 40 patients undergoing total knee arthroplasty (TKA) were selected. Inclusion criteria were patients over the age of 18 undergoing TKA under spinal anesthetic that were capable of signing informed consent.

Demographic data was collected including height, weight, BMI, and sex.

Postoperatively, while still under the effects of the spinal anesthetic, measurements were made of the patient's surgical leg from the skin to the adductor canal using a HLF50X 15-6 MHz transducer on a SonoSite SII ultrasound machine (Fujifilm, Toronto, ON). The adductor canal was identified with the transducer in the transverse plane on the patient's thigh and the transducer footprint marked on the skin and the leg circumference was measured. This location is where one would normally perform the ACB at our institution with the superficial femoral artery (SFA) roughly abutting the trough of the sartorius muscle. The SFA in the adductor canal was used as a reference point for measurement. The distance from the skin to the most superficial and nearest point of the SFA was measured in the following positions: 1) neutral, 2)

neutral position with manual lateral displacement of the skin, 3) 30 degree external rotation, 4) straight leg raised to 30 degrees and 5) knee and hip flexed to 90 degrees. For each position the ultrasound image was saved and a measurement from the upper lateral corner of the image to the SFA was taken and recorded. A single operator (MT) performed all scanning and measurement, while a single assistant facilitated the various passive leg movements. The ultrasound transducer was kept in the premarked footprint and oriented perpendicular to the thigh to provide consistency.

Statistical Analysis Plan:

All data were tabulated using Microsoft Excel and difference in distance between the leg positions were calculated. The means of these distances were used to discover the 90% confidence interval in each of the leg positions relative to the neutral position. For the secondary objective the data were graphically tabulated relative to the patient's BMI and leg circumference. A line of best fit was then calculated using Excel.

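### Could the mean change from neutral be an average of absolute differences, and so show change even if nothing moved?

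*Combined protocol and SAP*

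**What the plan says.** The primary goal, under Objectives, is "to discover if there is significant change in the distance from the skin to the adductor canal" when the leg is moved. Background Information gives the hypothesis without a direction: "It is hypothesized that the SAC distance changes with leg movement". Each of the "40 patients undergoing total knee arthroplasty (TKA) were selected" is measured in neutral and in four other positions, with one recorded measurement described per position (Study Design and Methods).

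The Statistical Analysis Plan handles the primary question in two steps. First, the "difference in distance between the leg positions were calculated". Then: "The means of these distances were used to discover the 90% confidence interval in each of the leg positions relative to the neutral position". Neutral is therefore fixed as the reference. The plan gives no subtraction formula, order or sign convention, and no rule linking the interval to a conclusion of significant change.

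A secondary goal asks "if these changes in distance had any relation to the BMI and leg circumference", and the plan answers it with plots and a line of best fit: "For the secondary objective the data were graphically tabulated". The word absolute occurs once, under Objectives, where it describes the raw skin-to-canal distance and not a difference.

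**The concern.** Two quantities could be called the mean difference from neutral: the average of the signed changes, and the average of their sizes. They behave differently when nothing moves. Signed reading errors cancel, so their mean centres on zero. Sizes cannot be negative, so their mean is positive whenever there is any error, and an interval around it will nearly always lie above zero. If sizes had been averaged and the interval compared with zero, all four positions would show change whatever the truth.

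The text gives some excuse for the worry. The hypothesis has no direction, and the motive is catheter displacement, for which lengthening and shortening might both matter. The same quantity would feed the plots against BMI and leg circumference. There, a line through sizes could slope upward only because scatter is greater in larger legs.

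**Working it through.** The documents state no effect size, SD or power, so there is no figure of the plan's own to reproduce.

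**Inputs.** n = 40 (Study Design and Methods); 90% interval for each position against neutral (Statistical Analysis Plan); t(0.95, 39 df) = 1.685. Assumptions: independent normal reading errors with SD e per measurement, no true movement, and significance judged by whether the interval excludes zero.

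**Signed difference.** D is the difference of two readings, so its SD is √2·e = 1.414e and its mean is 0. The half-width is 1.685 × 1.414e / √40 = 0.377e. The interval excludes zero in 10% of trials per position (simulated 9.8% to 10.3%).

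**Absolute difference.**
- Mean: 1.414e × √(2/π) = 1.128e.
- SD: 1.414e × √(1 − 2/π) = 0.853e.
- Half-width: 1.685 × 0.853e / √40 = 0.227e.
- 90% interval: 0.901e to 1.355e, with the mean about 8.4 standard errors above zero.
- Simulation: zero excluded in 50,000 of 50,000 trials at every position.
- Coarse recording softens this only in a corner case: with readings rounded to 1 mm, the rate is 85% at e = 0.1 mm and 99.7% at e = 0.2 mm.

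For assumed e of 0.5, 1, 2 and 3 mm, noise alone gives a mean size of 0.56, 1.13, 2.26 and 3.39 mm.

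**If there is a real shift.** Let the true mean shift be d, in SDs of the change. Then E|D| = √(2/π)·exp(−d²/2) + d·(1 − 2Φ(−d)).

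| d | mean size | mean size ÷ true shift |
|---|---|---|
| 0.1 | 0.802 | 8.0 |
| 0.266 | 0.826 | 3.1 |
| 0.5 | 0.896 | 1.79 |
| 1 | 1.167 | 1.17 |
| 2 | 2.017 | 1.01 |

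The choice matters greatly for small shifts and hardly at all for large ones. The documents do not show which case applies.

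**Which reading does the text support?**
- The plan subtracts, averages, and reports relative to neutral. That describes a paired mean difference. Taking sizes is an additional transformation, and no sentence mentions it.
- With signed differences, the mean of the differences equals the difference of the two position means, so the plan's loose reference to means of distances relative to neutral is coherent. A mean of sizes has no such equality and would need to be spelled out.
- A hypothesis without direction is what a two-sided interval on a signed mean addresses. It does not point to sizes.
- Background Information speaks of relative changes, which does not fix a sign but does not suggest sizes either.

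**Secondary plots.** For normal changes centred on zero at every BMI, the slope of |D| on BMI is 0.798 times the slope of the SD on BMI, and the signed slope is 0. The artefact therefore needs both the unlikely reading and scatter that rises with leg size, a pattern the documents do not report.

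**The case for a change.** The strongest case for acting is that the omission is real, the failure would be complete, and the remedy is one sentence. Nothing elsewhere in the document settles the sign. An analyst who averaged sizes in a spreadsheet would contradict no line of the plan. With single readings and no repeat measurements described, nothing in the plan would separate movement from reading error.

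The omission, the arithmetic and the low cost of clarifying all stand. The step from omission to defect does not. Almost any plan that says mean difference without a formula could be faulted in this way, and the usual meaning of those words is the valid analysis. The claim of a fixed answer also needs a decision rule that the plan does not state.

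The signed mean has a limitation of its own: patients who move in opposite directions cancel. That is a reason to look at the spread of individual changes when reading the results. It is not evidence that sizes were averaged.

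**Conclusion.** No change to the plan is needed. Read in its ordinary sense, the analysis is a signed paired difference, position minus neutral, with a 90% interval for the average shift. That interval has its nominal 10% error rate per position when nothing moves. Writing the convention down would record what an analyst would do anyway. Because the document is written in the past tense, stating the subtraction order belongs in the results report.

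The large effect, a spurious mean of about 1.13e that nearly always excludes zero, would arise only if per-patient sizes had been averaged and then compared with zero. The documents suggest neither step. The figures assume normal, independent reading errors and no movement. This conclusion rests on the natural reading of the text, since the documents do not show the spreadsheet calculation itself.

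### The relation of distance change to BMI and leg circumference is analysed only by a graph and a fitted line, with no measure of uncertainty

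*Combined protocol and SAP*

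**What the plan says.** The Objectives section sets two secondary goals: to describe the absolute distance, and to learn "if these changes in distance had any relation to the BMI and leg circumference". The Statistical Analysis Plan covers the second goal in two sentences. The first is "For the secondary objective the data were graphically tabulated relative to the patient's BMI and leg circumference". The second is "A line of best fit was then calculated using Excel".

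For the primary comparison the same section does plan a measure of uncertainty: "The means of these distances were used to discover the 90% confidence interval in each of the leg positions relative to the neutral position". Nothing comparable is named for the fitted line, and neither the Objectives nor the Study Design and Methods section supplies it. The sample size is given in Study Design and Methods ("40 patients undergoing total knee arthroplasty (TKA) were selected"), with no rationale for precision or power.

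**The concern.** The goal is a question about association, and a fitted line on its own does not answer it. Least squares returns a nonzero slope in essentially any data set, whether or not a relation exists. The plan gives no interval, standard error, correlation, R-squared or test, and no rule for reading the slope. A chance slope could therefore be reported as a relation, and a real but modest one could be dismissed as flat.

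The plan also leaves open what is fitted. The methods list five leg positions, which give four changes from neutral. With two predictors there could be up to eight lines, yet the plan speaks of the data in general and of one line. A reader cannot tell whether changes or absolute distances are plotted, or how many lines were fitted before any were shown.

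**Working it through.** The plan gives no figure to reproduce: no expected correlation, standard deviation, error rate or sample-size derivation. The check therefore asks what a fitted line can show at the stated sample size. In simple regression, testing the slope is equivalent to testing Pearson's r, so r is used as a unit-free scale.

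**Inputs from the documents:** n = 40, one surgical leg each, hence 38 degrees of freedom; four changes from neutral; two predictors.

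**Assumptions:** bivariate normality, complete data, and the illustrative values of r below.

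**1. No true relation, one line.** The statistic is t = r × √(38 / (1 − r²)).
- At r = 0.20, t = 0.20 × √(38 / 0.96) = 1.258, two-sided p = 0.216. About 22% of samples show |r| above 0.20 by chance.
- The average |r| from chance alone is about 0.13.
- The critical |r| is t / √(t² + 38): 0.312 at two-sided 5%, and 0.264 at the 10% level that corresponds to a 90% interval.

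**2. A modest true relation (r = 0.30), one line.**
- In 200,000 simulated samples, |r| fell below 0.20 in 24.8%.
- Power at two-sided 5% by Fisher's z: atanh(0.30) × √37 = 0.3095 × 6.083 = 1.883, and Φ(1.883 − 1.960) = 0.469.

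**3. What an interval would show.** By Fisher's z the limits are tanh(atanh(r) ± z / √37), with 1/√37 = 0.1644.

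| Observed r | 90% CI | 95% CI |
|---|---|---|
| 0.20 | -0.07 to 0.44 | -0.12 to 0.48 |
| 0.30 | 0.04 to 0.52 | -0.01 to 0.56 |

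For r = 0.30 at 95%, for example, the z-scale limits are 0.3095 ± 1.960 × 0.1644 = -0.013 and 0.632, which transform to -0.013 and 0.559.

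**4. If all eight lines were fitted (a number the plan does not state).** This is the chance, with no true relation, that at least one |r| exceeds 0.312:
- Independent lines: 1 − 0.95⁸ = 0.337. This is an upper figure and not realistic, because the four changes share the same patients and the same neutral measurement.
- Simulated with assumed correlations of 0.5 among changes and 0.7 between BMI and circumference: about 25%.
- Simulated with 0.8 and 0.8: about 18%.

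The conclusion rests on steps 1 to 3. Step 4 only shows why every fitted line should be displayed.

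**The case against.** The strongest reply is that this is a minor, descriptive aim. The only stated hypothesis is that the distance changes with leg movement, and the argument about catheter migration rests on that alone. A scatter plot with a line is a legitimate description in a 40-patient observational study, and the scatter gives some informal sense of noise. The natural reading is that all the changes are plotted. The eight-line figures apply a 5% criterion that the plan never adopts. Intervals at this sample size would leave modest relations unresolved anyway.

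Much of this is fair, and it limits the weight of the point. The primary result does not depend on it, and the eight-line figures are illustrative. The core still stands. The goal asks whether a relation exists, and the plan does not label the analysis descriptive. Visible scatter does not quantify how far a slope is compatible with zero. Wide intervals are a reason to report them, because a bare line hides that imprecision.

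**Conclusion.** The concern holds. As written, the method cannot answer the secondary question: following it exactly leaves a chance slope indistinguishable from a real one. At n = 40, correlations of 0.20 to 0.30 are the range in which a line looks meaningful while its 95% interval still includes zero. At the 90% level, 0.30 just excludes zero and 0.20 does not, so the level must be stated.

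The figures assume normality and complete data on all 40 patients. The correlations are assumed because the documents give none. The consequence is confined to this secondary goal. It is a change that should be made, not one on which the study's main conclusion depends.

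**What to change.** State which quantities are plotted. For each of the four changes from neutral, fit one simple regression on BMI and one on leg circumference. Report every slope (mm per kg/m² and mm per cm), with r, and give a confidence interval at a stated level; 90% would match the primary comparison. Show all fitted lines, label them exploratory, and conclude neither a relation nor its absence from a line alone.

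No single position should be promoted to the main one now. The plan is written in the past tense, so the data may already have been seen.

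The cost is up to eight simple regressions on data already collected. Excel's LINEST function returns the slope's standard error, so no new software is needed. The drawback is that the intervals will be wide: power is about 47% for a true r of 0.30 at two-sided 5%, and 80% is reached only at a true r of about 0.43. Modest relations will remain unresolved, and the report should say so.
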